2.4.2 Prior, concomitant and post therapies

Prior and concomitant medications and significant non-drug therapies will be summarized through frequency tables according to their WHO ATC class and WHO generic term. Prior medications will be defined to be drugs taken prior to the first dose of study medication. Concomitant medications will be medications taken between the first and last day with study medication, excluding medications started on the last day of study medication. Medications which started prior to the first dose of study medication and continued thereafter will be counted in both summaries.

The number of transfusions and the total RBC transfused during the study (mL/kg) will be summarized by ethnicity groups and overall. The amount of RBC transfused denoted the amount of RBC contained in the blood, i.e. (amount of blood transfused [mL]) \times hematocrit / 100). For each transfusion, the amount of blood given, expressed in mL, will be divided by the last available weight to calculate the amount transfused in mL/kg. For each patient, the total RBC transfused over the whole study will be calculated, summing up the amount received at each transfusion. Only transfusion dates on or after start of ICL670 will be considered for this analysis.

Missing day information for start date of prior chelation therapy or start date of history of blood transfusions will be imputed by the 1st of the Month. If the month is missing it will be imputed by January.

Time since start of first chelation therapy/blood transfusion = (Screening Visit date – start of first chelation/transfusion date + 1)/365.25.

Relevant medical history and current medical conditions will be coded and frequencies summarized for patients in the safety analysis set.

2.5 Analysis of the primary objective

2.5.1 Primary endpoint

The trial is designed to assess the efficacy of deferasirox in patients with non-transfusion dependent thalassemia based on absolute change in LIC from baseline after one year of treatment. The analysis for primary objective was performed at one-year (data cut-off date : 03-Jan-2015). The study met its primary objective. The primary endpoint, absolute change in LIC (mg Fe/g dw) at Week 52 from baseline, was statistically significantly different from 0 (Paired T-test $p<0.0001$, two-sided). The absolute change in LIC at Week 52 from baseline had mean (SD) -6.68 (7.018) (mg Fe/g dw) and a 95% confidence interval (-7.91, -5.45) (mg Fe/g dw).

As done in previous studies within patients with transfusional iron overload, a normal distribution will be assumed for LIC absolute change.

LIC will be measured at screening (Visit 1), Week 24 (Visit 15) and Week 52 (Visit 25) in treatment year 1. The primary efficacy variable will be the absolute change from baseline in LIC at Week 52, i.e. the difference of LIC at Week 52 minus LIC at baseline.

The absolute change in LIC from baseline after one year of treatment will be analyzed using the FAS set.

The following estimates will be provided:

- point estimate of the absolute change at Week 52,
- the ordinary 2-sided 95% confidence interval,
- p-value (descriptive only).

Also, LIC values at Week 52 will be computed with their corresponding 95% CI.

Handling of missing values/censoring/discontinuations

In case of missing LIC at Week 52, the last available post-baseline LIC value before Week 52 will be used in the calculation of the primary endpoint. Patients without post-baseline LIC at or before Week 52 or baseline LIC will be excluded from the analyses.

Supportive analyses

In order to further assess the absolute change and the relative change in LIC from baseline at Week 52, the estimates and the 95% confidence intervals will be provided for the following proportions (In case of missing LIC at Week 52, the last available post-baseline LIC value before Week 52 will be used):

- The proportion of patients with an LIC decrease by at least 3 mg Fe/g dw from baseline (LIC decrease ≥ 3 mg Fe/g dw) at Week 52; i.e., proportion of LIC decrease ≥ 3 mg Fe/g dw = subjects with $((\text{baseline LIC} - \text{LIC at Week 52}) \geq 3)$ divided by total number of subjects
- The proportion of patients with an LIC decrease by at least 30% from baseline (LIC decrease $\geq 30\%$) at week 52. i.e., proportion of LIC decrease $\geq 30\% =$ subjects with $((100 * (\text{Baseline LIC} - \text{LIC at Week 52}) / \text{Baseline LIC}) \geq 30\%)$ divided by total number of subjects.

2.6 Analysis of secondary efficacy objective(s)

All p-values provided for the secondary efficacy endpoints will be considered as exploratory only.

2.6.1 Secondary endpoints

2.6.1.1 Response analysis in patients with baseline LIC>15 mg Fe/g dw

Subjects who achieved the target baseline LIC >15 mg Fe/g will be included in this analysis. The proportion of patients with baseline LIC >15 mg Fe/g dw achieving a post-baseline LIC <5 mg Fe/g dw during the study will be presented with a 95% confidence interval. The normal approximation will be used for the distribution, i.e. the confidence interval will be calculated as follows ([Agresti and Coull 1998](#)):

$$100 * (p + z_{0.975}^2 / 2n) \pm z_{0.975} * \sqrt{(p(1-p) + z_{0.975}^2 / 4n) / n} / (1 + z_{0.975}^2 / n)$$

Where p denotes the proportion, n the corresponding number of values, $z_{0.975}$ the 97.5% quantile of the standard normal distribution, and sqrt the square root function (see also [Brown, Cai, DasGupta, 2001](#)).

Time to the first LIC <5 mg Fe/g dw among patients with baseline LIC >15 mg Fe/g dw will be analyzed based on the Kaplan-Meier method. Kaplan-Meier curves for time to first LIC <5 mg Fe/g dw and the medians along with 95% confidence intervals will be presented.

If a subject does not achieve a first post-baseline LIC <5 mg Fe/g dw, the day of the last LIC assessment during the study will be used in the Kaplan-Meier analyses for censoring.

If the last assessment date will be incomplete, the earliest possible date will be imputed (first of month if day will be missing, first of year if both day and month will be missing). This imputation rule will be only used for the derivation of the last assessment day.

2.6.1.2 Long-term efficacy of treatment to target LIC of 3 mg Fe/g dw followed by one or more treatment holidays until the LIC is greater or equal to 5 mg Fe/g dw

Subjects who achieved the target LIC <3 mg Fe/g will be included in this analysis. Time from the target LIC <3 mg Fe/g dw to the first LIC ≥ 5 mg Fe/g dw in the follow-up period will be analyzed by using the Kaplan-Meier method. Kaplan-Meier curves for time to first LIC ≥ 5 mg Fe/g dw and the medians along with 95% confidence intervals will be presented.

If the subject does not have a first LIC ≥ 5 mg Fe/g dw in the follow-up period, the day of the last LIC assessment during the study will be used in the Kaplan-Meier analyses for censoring.

If the last assessment date will be incomplete, the earliest possible date will be imputed (first of month if day will be missing, first of year if both day and month will be missing). This imputation rule will be only used for the derivation of the last assessment day.

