7.2 Assessment types

7.2.1 Efficacy assessments

7.2.1.1 Liver iron content (LIC) assessment by MRI

[figure not shown]
Change in LIC from baseline after 52 weeks of treatment with study drug will be used as primary efficacy parameter. And, change in LIC from baseline after approximately six month intervals of treatment with study drug will be used as a secondary efficacy parameter.

LIC will be measured at Screening Visits 1 or 2, Visit 15 (week 24), Visit 25 (week 52), and approximately every six months thereafter (weeks 76, 104, 128, 156, 180, 208, 232, and 260) using a validated R2 MRI technique. All patients enrolled in the study will have MRI scans using a specific sequence. Raw image data will be analyzed centrally to determine the patient's LIC value. The result of the measurement will be provided to the sites by the central laboratory.

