10.5 Secondary objectives

10.5.1 Response analysis in patients with baseline LIC greater than 15 mg Fe/g dw

The proportion of patients with baseline LIC >15 mg Fe/g dw achieving an LIC <5 mg Fe/g dw during the study will be presented with a 95% confidence interval. The normal approximation will be used for the distribution, i.e. the confidence interval will be calculated as follows (Agresti and Coull 1998, formula (2)):

$$100 * (p + z_{0.975}^2 / 2n \pm z_{0.975} * \sqrt{(p(1-p) + z_{0.975}^2 / 4n) / n}) / (1 + z_{0.975}^2 / n)$$

Where p denotes the proportion, n the corresponding number of values, $z_{0.975}$ the 97.5% quantile of the standard normal distribution, and sqrt the square root function (see also [Brown, Cai, DasGupta, 2001](#)).

Time to the first LIC <5 mg Fe/g dw among patients with baseline LIC >15 mg Fe/g dw will be analyzed based on the Kaplan-Meier method. Kaplan-Meier curves for time to first LIC <5 mg Fe/g dw and the medians along with 95% confidence intervals will be presented.

10.5.2 Long-term efficacy of treatment to target LIC of 3 mg Fe/g dw followed by one or more treatment holidays until the LIC is greater or equal 5 mg Fe/g dw

Time from the target LIC <3 mg Fe/g dw to the first LIC \geq 5 mg Fe/g dw in the follow-up period will be analyzed by using the Kaplan-Meier method. Kaplan-Meier curves for time to first LIC \geq 5 mg Fe/g dw and the medians along with 95% confidence intervals will be presented.

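### Time to LIC <5 (SAP 2.6.1.1) is estimated by Kaplan-Meier on scans about six months apart; with no comparator, the median time to target runs late, by about 13 weeks on average, and its CI does not allow for this

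*SAP*

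**What the plan says.** Protocol 7.2.1.1 fixes the scan calendar. For the first year: "LIC will be measured at Screening Visits 1 or 2, Visit 15 (week 24), Visit 25 (week 52". After that, scans come "approximately every six months thereafter (weeks 76, 104, 128, 156, 180, 208, 232, and 260".

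SAP 2.6.1.1 covers patients who start above 15 mg Fe/g dw. Their time to the first LIC <5 "will be analyzed based on the Kaplan-Meier method", and "the medians along with 95% confidence intervals will be presented". For a patient who never reaches the threshold, "the day of the last LIC assessment during the study will be used in the Kaplan-Meier analyses for censoring". Protocol 10.5.1 has the same plan ("Kaplan-Meier curves for time to first LIC"). SAP 2.6.1.2 applies the same method to "Time from the target LIC <3 mg Fe/g dw to the first LIC ≥ 5 mg Fe/g dw in the follow-up period".

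Neither document defines the event date explicitly, but LIC exists only as a scan result, so the event date can only be a scan date. Neither mentions interval censoring, a midpoint rule or a sensitivity analysis for scan spacing. Protocol Table 3-1 and SAP Table 1-1 word the first endpoint as the time to 'achieving' the threshold, not as the time to its first documentation.

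**The concern.** A patient whose LIC is 5 or more at one scan and below 5 at the next crossed at an unknown time in between. Ordinary Kaplan-Meier treats the later scan date as the exact event time, so every observed crossing is dated late or, at best, on time.

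In a randomised comparison both arms would carry a similar delay and much of it would cancel. Here there is one arm, and the median is what will be read as the time a heavily loaded patient needs to reach the target. Amendment 1 added this endpoint because the earlier placebo-controlled trial was too short for such patients to reach the therapeutic target, so the absolute time is the information sought. Calling secondary p-values exploratory (SAP 2.6) does not help, because the issue is a reported median and interval, not a test.

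**Working it through.** Neither document states an expected median, a precision or a power for this endpoint, so there is no planned figure to reproduce.

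**1. Average delay.** Scheduled scans are at weeks 24, 52, 76, 104, 128, 156, 180, 208, 232 and 260 (Protocol 7.2.1.1). Counting from day 1, the gaps are five of 24 and five of 28 weeks, mean 26. If a crossing is equally likely at any time, the expected delay to the next scan is

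sum(gap²) / (2 × sum(gap)) = 5 × (576 + 784) / (2 × 260) = 6800 / 520 = 13.08 weeks, or 13.08 × 7 / 365.25 = 0.25 year.

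**2. Delay in the median.** In a large sample with scans on schedule, the Kaplan-Meier median is the first scan week at or after the true median. The shift therefore depends on position in the gap:

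- true median week 100, reported 104: 4 weeks late
- true median week 194, reported 208: 14 weeks late
- true median week 129, reported 156: 27 weeks late

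With scans on schedule the range is near 0 to 28 weeks. One missed scan makes a gap of 24 + 28 = 52 weeks.

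**3. Simulation at realistic sizes.** The documents do not give the number of patients with baseline LIC above 15 or the event-time distribution. Assumed: n = 30, 60 or 90; Weibull times with shape 2; true medians of 80, 100, 117, 130, 150 and 170 weeks; 5% annual loss; scans within 2 weeks of schedule; log-log CI; 2,000 runs per scenario.

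- Mean patient delay: 12.9 to 13.1 weeks.
- Average shift of the Kaplan-Meier median: 10.7 to 15.8 weeks.
- Coverage of the true median by the 95% CI, over the six true medians:

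| n | Scan dates | Exact dates |
|---|---|---|
| 30 | 65–95% | 94–96% |
| 60 | 35–96% | 95–96% |
| 90 | 15–95% | 95–96% |

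Coverage stayed at 93–96% for true medians of 80 and 130 weeks, and was worst at 100 weeks. There the curve is flat from about week 76 to week 104, at S(76) = exp(−ln 2 × 0.76²) = 0.67. With 90 patients and ignoring losses, the standard error is about √(0.67 × 0.33 / 90) = 0.05. The lower limit is then about 0.67 − 1.96 × 0.05 = 0.57, still above one half, so the CI for the median usually starts after week 100. More patients make this worse, because the interval tightens around a displaced step.

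**4. Does an interval-censored estimate help?** Two separate simulations with n = 60 and assumed Weibull times compared Kaplan-Meier with Turnbull medians. In one (300 runs for each of six true medians from 85 to 170 weeks), Kaplan-Meier was 10.9 to 14.4 weeks late and Turnbull, interpolated within its support interval, was within about 1.1 weeks of the truth. In the other, Kaplan-Meier was 10.7 to 16.0 weeks late and Turnbull was off by about −1 to +3 weeks. The SD was similar for both methods (in the first: Turnbull 9.6–17.4 weeks, Kaplan-Meier 9.7–18.8).

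**5. Measurement error.** With an assumed LIC measurement error of 10% or 20%, the mean delay falls to about 12.5 or 9.4 weeks, because noise sometimes takes a value below 5 early.

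**6. The second endpoint (SAP 2.6.1.2).** Let A and B be the true crossings below 3 and up to 5, and a and b the scans that show them. The error in the observed duration is (b − a) − (B − A) = (b − B) − (a − A), a difference of two delays of about 13 weeks each. With assumed median re-accumulation times of 40 to 100 weeks, the simulated net shift was −0.4 to −0.7 week, with an SD of about 11 weeks. If time is counted from scan a instead, only b is late, by 12.9 to 13.3 weeks on average.

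**The case against.** **Estimand.** LIC exists only as a scan value. If the endpoint means the first measured LIC <5, Kaplan-Meier with censoring at the last assessment is appropriate and its CI is not deficient for that quantity. This stands as far as it goes. But the SAP does not label the result that way, and its endpoint is the time to achieving the target. Labelling alone would remove the misreading without giving the time to target.

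**Size.** The 13 weeks is an average over patients and not the shift of any one median, and an example such as 129 against 156 is near the worst case. Ferritin below 300 ng/mL triggers an extra LIC scan (Protocol 6.4.2), and all post-baseline LIC values are used (SAP 2.1.1). These points stand and are why the size is given as a range.

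**Second endpoint.** A reader might infer that time from LIC <3 to LIC ≥5 is also a quarter of a year late. The documents do not support this as a general statement. It holds only if the clock starts at the scan showing LIC <3. That reading is plausible, since treatment is interrupted on a measured value, but the SAP does not state it. From crossing to crossing the two delays nearly cancel, and what remains is imprecision.

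**Consequence.** Both endpoints are secondary. This stands.

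**Conclusion.** The point holds for SAP 2.6.1.1 as a cheap improvement. Read as the time to achieving LIC <5, the planned Kaplan-Meier median is late by about 13 weeks on average, from near 0 to 28 weeks with scans on schedule, more with missed scans, and less with ferritin-triggered scans or LIC measurement error. Its nominal 95% CI can cover well below 95%, depending on where the true median sits between scans.

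The 13.08 weeks follows from the protocol's calendar if crossings are spread evenly within gaps. The shifts in the median and the coverage figures rest on assumed event times and sample sizes, so they illustrate the effect and do not predict it for this trial.

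A reader might infer that Kaplan-Meier is invalid here; it is valid for time to first documented LIC <5. The primary analysis and the responder proportion in 2.6.1.1 do not depend on this choice.

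**What to change.** **SAP 2.6.1.1.** Add a Turnbull non-parametric maximum-likelihood curve and median with a 95% CI. For each responder, use the interval from the last scan before the crossing to the first scan showing LIC <5. Non-responders stay right-censored at their last scan. Keep the Kaplan-Meier curve and label it 'time to first documented LIC <5'.

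**SAP 2.6.1.2.** State that the clock starts at the scan showing LIC <3. Treat only the LIC ≥5 event as interval-censored from that observed origin, and label the Kaplan-Meier result 'time to first documented LIC ≥5'. Make no claim about crossing-to-crossing time, which would need a method for two interval-censored ends.

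**Cost.** A small amount of programming on scan dates already collected. The CI needs a bootstrap or a built-in routine, and the Turnbull median may have to be reported as a range between two scan weeks.

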The risk of toxicity of deferasirox may be increased when inappropriately high doses are prescribed to patients with a low iron burden or with SF levels that are only slightly elevated. Detailed information regarding the correlation of toxicities and PK parameters (drug concentrations, C_{max}) is provided in the current [Investigators' Brochure].

A study of deferasirox was conducted in NTDT patients. Study No ICL670E2209, the THALASSA study, was a prospective, randomized, double-blind, placebo controlled trial of deferasirox with starting doses of 5 and 10 mg/kg/day in patients with NTDT.

The primary objective of this trial was to compare the efficacy of the two treatment groups of deferasirox based on the change in LIC (R2 MRI) from baseline after one year of treatment compared to placebo treated patients. One hundred and sixty-six patients with thalassemia intermedia (n=95), α -thalassemia (n=22) or HbE/ β -thalassemia (n=49) were randomized to starting deferasirox doses of 5 mg/kg/day (n=55) or matching placebo (n=28) and 10 mg/kg/day (n=55) or matching placebo (n=28). The average actual deferasirox dose (mean \pm SD) was 5.6 \pm 1.4 and 11.5 \pm 2.9 mg/kg/day, respectively. The primary objective of this trial was met. After one year of treatment with deferasirox, LIC significantly decreased by -1.95 mg Fe/g dw (95% CI: -2.94, -0.96; BL: 13.11) and -3.80 mg Fe/g dw (95% CI: -4.76, -2.85; BL: 14.56) in the deferasirox 5 and 10 mg/kg/day groups, respectively, compared with an increase of 0.38 mg Fe/g dw (95% CI: -0.59, 1.34; BL: 15.94) in the placebo; the difference between deferasirox 5 and 10 mg/kg/day groups vs placebo was significant (-2.33 mg Fe/g dw, $P=0.001$ and -4.18 mg Fe/g dw, $P<0.001$, respectively). After one year of treatment, the percentage of patients with LIC decrease ≥ 3 mg Fe/g dw from baseline was greater in the deferasirox 5 and 10 mg/kg/day cohorts (32.7% and 56.4%) compared to placebo (10.7%). In addition, more patients in deferasirox 5 and 10 mg/kg/day cohorts achieved LIC reduction $\geq 30\%$ from baseline (25.5% and 49.1%) compared to placebo (1.8%). The significant difference in the change in LIC from baseline between the 5 and 10 mg/kg/day group, -1.95 vs -3.80, $p=0.009$, justifies the starting dose of 10 mg/kg/day in this trial.

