7.1.6 Follow up period

All patients who discontinue study treatment before completing the study must have safety evaluations for 30 days after the last dose of study treatment.

Patients lost to follow up must be recorded as such on the CRF. For patients who are lost to follow-up, the investigator must show "due diligence" by documenting in the source documents steps taken to contact the patient, e.g., dates of telephone calls, registered letters, etc.

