Cmax	Maximum (peak) observed plasma concentration after single dose administration
CSR	Clinical Study report
CTCAE	Common Terminology Criteria for Adverse Events
DMC	Data Monitoring Committee
dw	Dry weight
ECG	Electrocardiogram
eCRF	Electronic Case Report/Record Form
EOS	End of study
FAS	Full Analysis Set
FE	Iron
FSH	Follicle stimulating hormone
GGT	Gamma glutamyl transferase
HbE	Hemoglobin E
HbH	Hemoglobin H
LDH	lactase dehydrogenase
LH	Luteinizing hormone
LIC	Liver iron content
LPLV	Last patient last visit
MedDRA	Medical Dictionary for Drug Regulatory Affairs
MRI	Magnetic resonance imaging
NTDT	Non-transfusion-dependent thalassemia
o.d.	Once Daily
OS	Overall Survival
PedsQL™	Pediatric Quality of Life Inventory™
PFS	Progression-Free Survival
PK	Pharmacokinetics
PPS	Per-Protocol Set
PRO	Patient-reported Outcomes
qd	Qua'que di'e / once a day
QoL	Quality of Life
RAP	Report and Analysis Process
RECIST	Response Evaluation Criteria in Solid Tumors
SAE	Serious adverse event

SAP	Statistical Analysis Plan
SD	Standard deviation
SF	Serum ferritin
SF-36	Medical Outcomes study short form-36
SF-6D	Short-Form Six-Dimension
SOC	System Organ Class
THALASSA	Novartis Study CICL670E2209
TFLs	Tables, Figures, Listings
Tmax	Time to reach maximum (peak) plasma concentration after single dose administration
TSH	Thyroid stimulating hormone
WHO	World Health Organization

1 Introduction

CICL670E2419 is a phase IV open label, multi-center, efficacy and safety study of deferasirox in iron overloaded patients with non-transfusion dependent thalassemia. This open-label, single-arm, multi-center 5-year study was designed to evaluate the efficacy and safety of deferasirox in iron overloaded NTDT patients, at least ten-years-old. A 1-year analysis was performed to assess the primary objective and selected secondary objectives. This study enrolled 134 patients including 68 Chinese and 66 non-Chinese, with 112 patients still on treatment at the time of the 1-year primary analysis.

The primary objective of this one-year analysis was met, confirming activity of deferasirox in the NTDT population, as observed in Study ICL670A2209. The absolute change in LIC from Baseline to Week 52 was statistically significantly different (Paired T-test, $p<0.0001$, two-sided). The absolute mean change in LIC (mg Fe/g dw) from Baseline to Week 52 was -6.68 (SD 7.018) with a 95% CI (-7.91, -5.45).

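### Time to LIC <5 in patients with baseline LIC >15: read as the share of all such patients reaching target, the Kaplan-Meier curve is too high, and a cumulative-incidence curve should stand beside it

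*SAP*

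**What the plan says.** Protocol section 3 sets one secondary objective for patients with baseline LIC above 15: the proportion who reach LIC below 5, and the time to reaching it. The plan covers both parts.

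- **Proportion.** SAP 2.6.1.1 takes the patients "achieving a post-baseline LIC <5 mg Fe/g dw during the study will be presented with a 95% confidence interval".
- **Time.** In the same section: "Time to the first LIC <5 mg Fe/g dw among patients with baseline LIC >15 mg Fe/g dw will be analyzed" by Kaplan-Meier, with curves and medians. Protocol 10.5.1 says only that it "will be analyzed based on the Kaplan-Meier method" and gives no censoring rule.
- **Censoring.** The SAP supplies the rule. For patients who never reach the target, "the day of the last LIC assessment during the study will be used in the Kaplan-Meier analyses for censoring". It makes no distinction by reason for leaving.

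A patient who stops drug has an end-of-treatment visit (Protocol 7.1.5), and Table 7-1 includes an LIC scan at that visit. Protocol 7.1.6 then requires only this: "All patients who discontinue study treatment before completing the study must have safety evaluations for 30 days after the last dose of study treatment". There is an exception. Under Protocol 7.1.5 a patient may stop drug and stay on study, and SAP 2.1.1 keeps all post-baseline LIC values in the efficacy analyses.

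Neither document names an estimand, a competing event or a sensitivity analysis for this endpoint. SAP section 4 declares no change from the protocol.

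**The concern.** Kaplan-Meier treats a censored patient as still able to have the event, at the same rate as those who remain under observation. A patient who stops drug above LIC 5 and has no further scan cannot have an LIC below 5 recorded in the study. The curve nevertheless passes that patient's weight to those who stay.

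The result is an estimate for a cohort in which nobody leaves. A reader who sees the curve and median next to the response proportion will probably take them as the share of heavily loaded patients who got to target, and when. With no control arm, nothing else shares the inflation. Amendment 1 added this objective because the earlier trial was too short for these patients to reach target, so the timing is what is new here.

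**Working it through.** **1. Stated figure.** There is none to reproduce. Protocol 10.9 marks power for key secondary variables as not applicable, and neither document gives an expected response or median for this endpoint.

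**2. Stopping rate (all patients, not this subset).** SAP section 1 reports 134 enrolled, "with 112 patients still on treatment at the time of the 1-year primary analysis". So 134 − 112 = 22 were off treatment, and 22/134 = 16.4%.

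- If that is one year's loss, the hazard is −ln(112/134) = 0.18 per year.
- One year is doubtful. The data cut-off was 03-Jan-2015 (SAP 2.5.1), and Amendment 1 expected the planned 117 to be enrolled by December 2013, so many patients could have had longer exposure.
- Amendment 2 (released 04-Sep-2014) counts 19 discontinued, leaving 115. Going from 115 to 112 in about 0.33 years gives −ln(112/115)/0.33 = 0.08 per year. This assumes that both counts use one definition and that the release date fits the count.

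I use 0.05 to 0.18 per year, with 0.18 as the upper end.

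**3. Constant-hazard comparison.** Let λ be the hazard of reaching LIC <5 (assumed 0.25 per year, with no source in the documents) and μ the stopping hazard.

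- Kaplan-Meier at 5 years: 1 − exp(−5λ) = 1 − exp(−1.25) = 71.3%.
- Cumulative incidence at 5 years: λ/(λ+μ) × [1 − exp(−5(λ+μ))].
- Kaplan-Meier median: ln 2/λ = 2.77 years.
- Cumulative-incidence median: −ln[1 − 0.5(λ+μ)/λ]/(λ+μ).

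| μ per year | Kaplan-Meier, 5 y | Cumulative incidence, 5 y | Gap (points) | Kaplan-Meier median (y) | Cumulative-incidence median (y) |
|---|---|---|---|---|---|
| 0.05 | 71.3% | 64.7% | 7 | 2.77 | 3.05 |
| 0.08 | 71.3% | 61.2% | 10 | 2.77 | 3.27 |
| 0.10 | 71.3% | 59.0% | 12 | 2.77 | 3.44 |
| 0.18 | 71.3% | 51.4% | 20 | 2.77 | 4.57 |

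For λ from 0.15 to 0.50 and the same span of μ, the five-year gap runs from 5 to 21 points.

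**4. Same comparison on the scan schedule** (Weeks 24 to 260), stopping at 16.4% per year:

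| Assumed 5-year Kaplan-Meier | Cumulative incidence | Kaplan-Meier median | Cumulative-incidence median |
|---|---|---|---|
| 30% | 19% | not reached | not reached |
| 50% | 33% | not reached | not reached |
| 70% | 48% | Week 156 | not reached |
| 80% | 56% | Week 128 | Week 180 |

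For five-year Kaplan-Meier values from 30% to 90%, the gap is 4 to 8 points at 5% stopping per year and 11 to 24 at 16.4%. In every case Kaplan-Meier is the higher figure and its median is never the later one.

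**5. The other target: response had nobody stopped.** I simulated 8,000 patients with baseline 15 plus an exponential excess of mean 7, exponential LIC decline with median rate 0.3 per year (log SD 0.6), and stopping at 16.4% per year.

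- Stopping independent of response: Kaplan-Meier 0.55 against a true 0.54.
- Slower half stopping at 1.5 times the average hazard and faster half at 0.5 times: 0.67 against 0.53.

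For this target, the bias depends on whether poor responders leave more often.

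**The case against.** Several points on the other side are sound.

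- **The response rate is already planned.** The crude proportion keeps patients who stop in its denominator. One might infer that the plan fails to deliver the response rate its objective asks for; it does not fail. What the proportion lacks is timing.
- **Kaplan-Meier is not wrong for every target.** A reader might infer that the censoring is informative and the curve biased outright. For response had all stayed on treatment, that needs stopping to depend on response. The documents make a link plausible: the dose may rise further while LIC stays above 15 (Protocol 4.1), several reactions are described as dose-dependent (1.2.1.2), and adverse events are a listed withdrawal reason (6.5.2). They do not show one.
- **Stopping does not rule out later response as death does.** The earlier trial's placebo arm is reported in Protocol 1.2.1.2 as "compared with an increase of 0.38 mg Fe/g dw", and in Table 10-3 as a mean change of +0.26 (SD 3.501). That is another trial's mean, and patients who leave may be chelated elsewhere: Protocol 6.2 bars other chelators only while they are enrolled. That a patient who stops has almost no chance of reaching the target is therefore not established. The narrower fact remains that without a further scan no response can be recorded.
- **Censoring is at the last LIC, not at treatment stop.** Patients who stay on study off drug keep contributing. How many do so is not documented.
- **Some exits are reasonably censored.** Loss to follow-up and administrative problems are listed reasons for leaving. Making every discontinuation a competing event would count these as certain non-response.
- **The endpoint is secondary.** It is unpowered, and SAP 2.6 calls the secondary p-values exploratory. That label does not change what the curve and median appear to say.

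**Conclusion.** The concern holds in a limited form. Against the share of all patients with baseline LIC >15 who reach LIC <5 over time, Kaplan-Meier under this censoring rule is never lower. It is too high once patients have left without further scans and others respond later. Its median, if reached, is the same or too early. Nothing in either document corrects this.

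The direction follows from the rule; the size cannot be derived from the documents. The number with baseline LIC >15, and their response and stopping rates, are not given. The 7-to-20-point gap at five years, and the median of 2.8 years against 3.1 to 4.6, rest on an assumed target hazard of 0.25 per year, constant hazards, and stopping of 0.05 to 0.18 per year taken from or set around whole-study counts. A reader might carry the upper figure forward as the expected error, but the documents do not support 0.18 per year for this subset or beyond the first year.

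This is a cheap improvement to a secondary analysis. It does not invalidate the planned curve.

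**What to change.** In SAP 2.6.1.1:

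1. **State the target of each display.** Keep the Kaplan-Meier curve and median, labelled as the estimate had patients stayed on treatment.
2. **Add the Aalen-Johansen cumulative incidence of first LIC <5**, with 95% CI at Weeks 52, 104, 156, 208 and 260, and the time at which it reaches 50% or 'not reached'.
3. **Competing events:** death, and permanent discontinuation for adverse event, abnormal laboratory value or test result, or lack of response (where recorded; Protocol 6.5.2 does not list it), when no further LIC is obtained.
4. **Still at risk:** patients who stop drug but continue LIC scans. Count their later values, in line with Protocol 7.1.5 and SAP 2.1.1.
5. **Censor** loss to follow-up, administrative exit and end of study. Assign the remaining reasons, such as withdrawn consent or protocol violation, before the final analysis.
6. **Sensitivity analysis:** treat all discontinuations as competing.

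No new data are needed, because the End of Treatment eCRF already records the date and reason for stopping (Protocol 6.5.1). The cost is SAP wording, one extra output with its sensitivity run, and a possibly less favourable figure.
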